4.6.2 Additional criteria - carbohydrate metabolism

Absolute values as well as absolute and relative changes from baseline for fasting plasma glucose, OGTT parameters, fasting insulin, and HbA_{1c} values will be summarized descriptively by visit.

The effect of Omnitrope[®] treatment on HOMA and QUICKI scores, calculated subsequent for each plasma glucose and insulin measurement, will be evaluated at each visit using descriptive statistics for the observed values along with the absolute and relative changes from baseline.

HbA_{1c}, glucose and insulin data will be listed per parameter, center and patient number and will include: visit, sample date/day, fasting status, parameter result in CRF and SI unit, reference range in CRF and SI unit, outside reference range indicator, clinical significance and a column containing comments. Results of OGTT will be listed by center, patient number and will include: visit, sample date/day, fasting glucose at baseline (-10 minutes) and at 120 minutes in CRF and SI unit, a column providing if diabetes mellitus was diagnosed during OGTT, and comments. Assessed HOMA and QUICKI scores will be listed by center, patient number and visit. Additionally, fasting status and sample date/day will be provided.

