2.3 Endpoints

2.3.1 Primary Endpoint

The development of diabetes is the primary endpoint of the study and is evaluated on the basis of the carbohydrate metabolism (fasting plasma glucose (FPG) and oral glucose tolerance test (OGTT)).

Specifically of interest is, number and percentage of patients developing overt type II diabetes mellitus after the end of GH treatment, characterized by fulfilment of the following criteria:

- FPG \geq 126 mg/dl (7.0 mmol/l) during blood sampling and/or during OGTT
- 2-h plasma glucose \geq 200 mg/dl (11.1 mmol/l) during OGTT

Documented confirmation on diagnosis of diabetes mellitus by investigator during OGTT will also be considered to qualify incidence of elevated glucose values as development of overt type II diabetes mellitus.

Fasting plasma glucose as well as an OGTT will be measured at baseline (i.e. final visit of EP00-401), 6 months, 1, 5 and 10 years after the end of treatment.

Additional criteria – carbohydrate metabolism

Additionally, long term effect of growth hormone (GH) treatment on carbohydrate metabolism is also assessed by

- Change from baseline in FPG, baseline and 2hr plasma glucose (during an OGTT), fasting plasma insulin and glucose glycosylated hemoglobin (HbA_{1C}) at 6 months, 1, 5 and 10 years after the end of treatment.

- **Insulin resistance** will be estimated at baseline, 6 months, 1, 5 and 10 years after the end of treatment, using both the homeostasis model assessment (HOMA; Matthews et al. 1985) and quantitative insulin sensitivity check index (QUICKI; Katz et al. 2000):

$$\text{HOMA} = \frac{\text{fasting insulin } (\mu\text{U/ml}) \times \text{fasting glucose (mg/dl)}}{405.41^*}$$

*use constant 22.5 instead of 405.41 if glucose concentration is reported in mmol/L

$$\text{QUICKI} = \frac{1}{\log \text{fasting insulin } (\mu\text{U/ml}) + \log \text{fasting glucose (mg/dl)}}$$

Implausible insulin or glucose values will be excluded, i.e. Glucose values below 0.1 mmol/L and insulin values below 0.1 pmol/L will not be used for the calculation of HOMA and QUICKI.

Potential of GH-treatment induced insulin resistance will be captured through change from baseline in HOMA and QUICKI at 6 months, 1, 5 and 10 years after the end of treatment

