4.4.3 Concomitant medication

Information on administration of any medications, except investigational medicinal products, should have been reported in the appropriate section of the CRF, along with dose information, dates of administration and reason for use. Any diagnostic, therapeutic or surgical procedure should have also have been recorded, including the date, indication, descriptions of the procedure and clinical findings.

Concomitant medication will be coded according to WHO-DRL. For version and used update strategy for coding see coding guideline for this study. All documented concomitant medication data will be summarized separately by Anatomical Therapeutic Chemical (ATC) term (level 2) and preferred term, providing the number and % of patients to whom medication was administered. This summary will be prepared for the FAS analysis set.

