4.6 Analysis of primary endpoint

Patients in the safety set (SAF) are considered for analyzing the primary endpoint (and related endpoints).

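### If any patient starts insulin or another glucose-lowering drug, section 4.6.2 has no rule to separate those samples, and HOMA and QUICKI under insulin would enter summaries read as a growth hormone effect

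*SAP*

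**What the plan says.** Section 4.6.2 deals with the additional carbohydrate-metabolism criteria. For fasting plasma glucose (FPG), OGTT parameters, fasting insulin and HbA1c, the "values will be summarized descriptively by visit", both as observed and as change from baseline. HOMA and QUICKI are "calculated subsequent for each plasma glucose and insulin measurement, will be evaluated at each visit using descriptive statistics". Section 4.6 places these analyses in the safety set, which includes patients who develop diabetes.

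The SAP attributes the result to growth hormone. Section 4.6.2 calls it "The effect of Omnitrope[®] treatment on HOMA and QUICKI scores", and section 2.3.1 states: "Potential of GH-treatment induced insulin resistance will be captured through change from baseline in HOMA and QUICKI".

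Section 2.3.1 gives the only value-level exclusion, and it applies to HOMA and QUICKI alone: "Glucose values below 0.1 mmol/L and insulin values below 0.1 pmol/L will not be used for the calculation of HOMA and QUICKI".

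Section 4.4.3 expects each medication to be recorded with its dose, dates and reason. The only use it describes is a frequency table: "All documented concomitant medication data will be summarized separately by Anatomical Therapeutic Chemical (ATC) term (level 2) and preferred term". Section 2.7 plans no subgroups, section 3 drops the per-protocol analysis, and section 4.8 has no rule for values obtained after glucose-lowering treatment begins. The listings in section 4.6.2 carry fasting status, sample date, clinical significance and comments, and for the OGTT whether diabetes was diagnosed. They have no column for drug status.

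**The concern.** The study exists to find patients who develop diabetes. Glucose-lowering treatment is a foreseeable consequence of that event, and the visits at 1, 5 and 10 years leave long gaps in which it could start.

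Two different problems then arise:

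- **Under injected insulin**, measured insulin may include the drug, or the drug may suppress the patient's own insulin without being measured by the assay. In either case HOMA and QUICKI no longer estimate insulin resistance.
- **Under any glucose-lowering drug**, FPG, 2-h glucose, fasting insulin and HbA1c are real measurements, but they partly reflect that drug.

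As written, both kinds of value enter the visit means and the changes from baseline without a mark, and the result is described as the effect of growth hormone. A reader of the planned tables could not tell which values were on drug.

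**Working it through.** The SAP states no sample size, event count or expected metabolic value for this point, so there is no plan figure to reproduce. The check has two parts.

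**1. Does any rule separate on-drug samples?** Sections 2.3.1, 2.6, 2.7, 3, 4.4.3, 4.6, 4.6.1, 4.6.2 and 4.8 were read for one. None does. The SAP does not use the word pooling; it follows from summarising every measurement in the whole safety set.

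**2. How large could the effect be?** All patient values below are assumed. The formulas are those of section 2.3.1, with log taken to base 10 (the SAP does not state the base):

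- HOMA = insulin (µU/ml) × glucose (mg/dl) / 405.41
- QUICKI = 1 / (log insulin + log glucose)

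| Assumed patient | Insulin | Glucose | HOMA | QUICKI |
|---|---|---|---|---|
| Non-diabetic | 10 | 88 | 2.17 | 0.340 |
| Diabetic, untreated | 25 | 160 | 9.87 | 0.278 |
| Same patient, oral drug | 12 | 105 | 3.11 | 0.323 |
| Same patient, insulin seen by assay | 60 | 120 | 17.76 | 0.259 |
| Same patient, insulin not seen by assay | 3 | 120 | 0.89 | 0.391 |

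Under insulin the same patient's HOMA is 17.76 or 0.89, depending on the assay. In the second case the patient looks more insulin-sensitive than the non-diabetic one.

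*Visit means with 100 patients, 3 of them diabetic.* Mean = (97 × non-diabetic value + 3 × diabetic value) / 100.

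| State of the 3 diabetics | Mean HOMA | Difference from untreated | Mean FPG (mg/dl) |
|---|---|---|---|
| Untreated | 2.40 | – | 90.2 |
| Oral drug | 2.20 | -0.20 | 88.5 |
| Insulin, seen by assay | 2.64 | +0.24 | 89.0 |
| Insulin, not seen by assay | 2.13 | -0.27 | 89.0 |
| Left out altogether | 2.17 | -0.23 | 88.0 |

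For 50 to 150 patients with 1 to 5 treated, the shift from the untreated course runs as follows:

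- Mean HOMA: from 5 × (0.89 - 9.87)/50 = -0.90 to 5 × (17.76 - 9.87)/50 = +0.79.
- Mean FPG: from (120 - 160)/150 = -0.3 to 5 × (105 - 160)/50 = -5.5 mg/dl.

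*A single patient.* With insulin 60 and glucose 140, HOMA = 60 × 140/405.41 = 20.72. Added to 49 patients with mean 2.0, the mean is (49 × 2.0 + 20.72)/50 = 2.37, a rise of 19%. An HbA1c 1.5 points below its untreated level shifts the mean by -1.5/50 = -0.03 at n = 50, or -1.5/10 = -0.15 at n = 10.

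**The case against.** **On-drug samples are not shown to exist.** This stands. The SAP does not say that any patient took such a drug. Section 4.3 mentions withdrawal criteria whose content is in the protocol, which is not at hand. The point is therefore conditional.

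**The analysis is descriptive and robust statistics are reported.** This stands in part. Section 2.1 requires medians, quartiles and extremes. One HOMA of 20.7 among 50 values would hardly move the median and would show as the maximum. Means and changes from baseline are reported as well, however, and nothing in the tables would explain the outlier.

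**All observed values are a legitimate summary in long-term safety follow-up.** For glucose, fasting insulin and HbA1c this stands: they describe the patients as they were. It does not rescue HOMA and QUICKI under insulin, because the score no longer measures what section 2.3.1 says it captures.

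**Leaving on-drug samples out does not recover the untreated course.** This also stands. In the example, exclusion gives mean HOMA 2.17 against 2.40 untreated, further off than the 2.20 with oral-drug values included. Exclusion removes the patients who did worst, so it cannot be the main summary.

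**The listings already help.** Only in part: diagnosed patients and sample dates can be found, but drug status is not shown beside the laboratory values.

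**Conclusion.** The point holds in conditional form. If a patient starts a glucose-lowering drug, section 4.6.2 as written mixes on-drug with off-drug samples. Under insulin it also summarises HOMA and QUICKI values that do not estimate insulin resistance. The effect is on means and changes in supporting summaries: either direction for HOMA and QUICKI, mostly favourable for glucose and HbA1c. Under the assumptions above it ranges from negligible to about 0.9 HOMA units and 5.5 mg/dl in FPG. The true size depends on the number of treated patients, which is not known and may be zero.

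Two stronger readings are tempting and not supported. A reader might infer that the patients who did worst are known to make the metabolic course look better. The SAP does not show that such samples exist, and the single-patient HOMA example makes the course look worse. A reader might also infer that the primary result is biased. The diabetes count in section 4.6.1 has its own criteria and is not calculated from these visit summaries.

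**What to change.** In section 4.6.2:

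1. Flag each sample by date against concomitant glucose-lowering medication, and show the flag in the listings.
2. From the start of insulin treatment, list HOMA and QUICKI but leave them out of the visit summaries. Report how many values and patients were left out.
3. Keep the all-samples summary of FPG, 2-h glucose, fasting insulin and HbA1c as the main one. For HOMA and QUICKI, the main summary uses all samples not on insulin.
4. Add a supplementary summary without on-drug samples, with the number of on-drug patients at each visit.
5. State that the supplementary summary removes patients who worsened, does not recover the untreated course, and must be read with the diabetes count.

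The cost is SAP wording, one derived variable from data already collected, some repeated tables and a few values set aside. No patient procedure changes. If nobody was treated, the flag documents that.

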4.7 Analysis of secondary endpoints

4.7.1 Safety evaluations

4.7.1.1 Immunogenicity

The number and percentage of patients with positive anti-rhGH antibodies (ABs) will be tabulated by visit. For patients with positive anti-rhGH results, all results of anti-rhGH testing will be listed by center, patient number, and visit and will include: parameter, value, unit (if available), and assessment if positive or negative

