2.1 Study documents and general considerations

This document describes the procedures and conventions to be used in the final analyses with data of all patients who were included into study EP00-402.

The study is based on the

- study protocol V 1.0, dated 16 Mar 2007,
- Amendment no. 01, dated 12 Mar 2012 incorporated into protocol v 1.0 leading to protocol v 2.0, dated 12 Mar 2012,
- Amendment no. 02, dated 9 May 2012 incorporated into protocol v2.0 leading to protocol v3.0, dated 9 May 2012,
- Amendment no. 03, dated 6 Jun 2013 incorporated into protocol v3.0 leading to protocol v 4.0, dated 6 Jun 2013,
- Amendment no. 04, dated 14 July 2014 incorporated into protocol v4.0 leading to protocol v5.0, dated 14 July 2014.

This study was terminated by the sponsor [REDACTED] Following decision of [REDACTED] study termination all patients were called in for a last visit (documented on the final visit page of the case report form (CRF)).

Raw data listings, summary tables, graphs and statistical tests will be generated by means of the program SAS 9.3 or higher.

The following descriptive statistical parameters will be shown in summary tables

- Continuous variables: n (valid cases), n (missing data), mean, median, standard deviation (SD), min, max, quartiles
- Categorical variables: Count and percentage of category. Percentages are routinely based on the total category count excluding the missing category if not otherwise mentioned. Percentages showing a rate relative to the total number of patients in this group are given in special tables (e.g. Adverse Event (AE) tables). Footnotes will specify the percent basis.

For continuous variables, if not otherwise specified, mean, median and quartiles will be reported to one decimal place greater than the precision of data as collected. Standard deviation will be

presented in two decimal place greater than the data and minimum/ maximum values will be reported with the same precision, as they were collected. This rule is only valid if values are not converted for the summary.

Generally, percentages will be displayed in the format xx.d, i.e. one decimal place will be shown; if the calculated percentage is 100, no decimal is required (i.e. 100% and not 100.0%). If the count is zero no percentage needs to be shown.

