2.3.2 Secondary Endpoints

2.3.2.1 Safety endpoints

Criteria for assessing long term safety of GH treatment focusing on the secondary objectives are:

- **Immunogenicity:** Number and percentage of patients developing anti-rhGH antibodies through the follow-up period after end of GH treatment is the secondary safety endpoint associated with monitoring and assessing immunogenicity.

Patients will be screened for anti-rhGH antibodies at baseline and 6 months after the end of treatment. Only in case of positive antibodies measurements in previous visit follow-up measurements are planned after 1 year, 5 years and 10 years. Positive antibodies are defined as values above 1.76. Unscheduled visits will be excluded from the analysis.

- **Laboratory evaluations – safety parameters:** Change from baseline (Shift from baseline, as applicable) at 6 months, 1 year, 5 years and 10 years after end of GH treatment in laboratory safety parameters as follows:
 - **Hematology:** Hemoglobin, hematocrit, white blood cell count (WBC, total and differential), red blood cell count (RBC), platelet count, mean cell volume (MCV), mean cell hemoglobin (MCH), mean cell hemoglobin concentration (MCHC), erythrocyte sedimentation rate (ESR).
 - **Biochemistry:** Creatinine, urea, aspartate aminotransferase (AST), alanine aminotransferase (ALT), gamma-glutamyltransferase (gamma-GT), alkaline phosphatase, total bilirubin, albumin, total protein, HDL, LDL, sodium, potassium, chloride, uric acid, fasting total cholesterol, fasting triglycerides, calcium, phosphorus.
 - **Thyroid function:** Free thyroxine and thyroid stimulating hormone.
 - **Urinalysis:** pH, glucose, ketones, bilirubin, protein.

- Number and percentage of patients with Adverse Events and Serious Adverse Events
- Change from baseline in vital signs parameters (blood pressure, pulse rate) and body weight, BMI, and BMI SDS will be assessed at each visit (baseline, 6 months, 1, 5, and 10 years after termination of treatment). BMI is calculated by [weight in kg] divided by [height in m]². For further details on the calculation of BMI SDS, see Section 5.1.
- Number and percentage of patients with significant finding in any body systems: head (external), eyes, ears, nose and throat, lungs, cardiovascular system, abdomen, musculo-skeletal system, skin, lymph nodes, central nervous system, and where appropriate, others. Physical examinations are performed at baseline, 6 months, 1 year, 5 and 10 years after end of treatment.

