4.1 General considerations

Data transfer from EP00-401

Some information for analyses planned in the protocol is not provided in the CRF of this follow-up study, but in the CRF of study EP00-401 only. Therefore, the following variables provided in the CRF of EP00-401 will be transferred to this study:

- age at final visit
- gender and race
- physical examination and pubertal status at final visit
- height, height Standard Deviation Score (SDS) at final visit
- weight and BMI, BMI SDS at final visit
- fasting plasma glucose, OGTT results, fasting plasma insulin, HbA_{1C} at final visit
- IGF-I, IGFBP-3, IGF-1 SDS, and IGFBP-3 SDS at final visit
- anti-rhGH antibody testing at final visit
- safety lab at final visit
- blood pressure and pulse at final visit
- exposure to study drug

Data of study EP00-401 will be transferred to EP00-402 on the same date the EP00-402 database is locked. In general, analysis data (i.e. data created for the analysis of EP00-401) will be transferred not the original CRF data.

Study days, baseline and visits

Study days are defined as date of assessment minus date of baseline visit.

Baseline is defined as final visit of study EP00-401. If no date of final visit is available, the date of F0 baseline visit of study EP00-402 will be used instead.

Analyses by visits will be based on CRF visits, i.e. F1 Month 6, F2 1 Year, F3 5 Years, and F4 10 Years/Final. The CRF visit F4 10 Years/Final will be presented as EOS (termination visit).

Conversion factors for laboratory parameters

In order to harmonize laboratory results by using the same units, some laboratory results will be converted. Corresponding conversion factors will be listed by parameter and will provide CRF unit, SI unit and conversion factor. If albumin is given in %, the respective values will be converted to g/l using total protein values.

[figure not shown]

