4.7.1.2 Safety parameters - Laboratory evaluations

Change from baseline (Shift from baseline) in hematology, biochemistry, thyroid function, and urinalysis parameters will be displayed by visit using descriptive statistics and/ or frequency tables depending on the type of variable (continuous or discrete).

4.7.1.3 (Serious) Adverse events

AEs are coded according to Novartis MedDRA, Version 19.1 or higher.

Only adverse event starting or worsening during study EP00-402 will be presented. Adverse events with missing or incomplete start dates not clearly attributable as starting/worsening prior to study EP00-402 will be included in the analysis.

A general summary table of AEs will contain the total number of AEs, the total number of SAEs, and separate descriptions of the splits for the variables relationship to study drug, action taken, outcome and intensity.

The incidence of an AE is defined as the number of patients who experience that event, divided by the number of patients in the SAF population. With AE incidence, each event will be counted only once for a given patient. More specifically, if a patient reports the same event more than

once, as determined by preferred term and system organ class, that patient will be counted only once for the incidence of the AE. For example, when a patient reported three instances of headache, this patient counts only once towards the total incidence of headache. Incidence of events within a system organ class is defined similarly. Whenever incidence is cross-tabulated with intensity in the summary tables, the incidence of an AE will be calculated for each level of intensity, i.e., the number of patients who experience that AE on a certain level of intensity.

The occurrence of an AE is defined as the total number of times the event occurs in the SAF population. With AE occurrence, a patient may contribute more than once to the total occurrence count. More specifically, if a patient reports a particular event, as determined by preferred term and system organ class (and having removed duplicate reporting of the same event) more than once, each event will count once towards the total event occurrence. Using the above example, headache would be counted three times for the patient who reported three separate occurrences of headache.

Occurrence tables will provide information about rates of AEs per patient-year, calculated as $12 \times \{(\text{number of events}) / (\text{months of study exposure})\}$.

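### The immunogenicity endpoint is new antibody development after treatment, but the SAP tabulates only positivity by visit

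*SAP*

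**What the plan says.** Section 2.3.2.1 gives the endpoint as "Number and percentage of patients developing anti-rhGH antibodies through the follow-up period after end of GH treatment". The related objective in section 2.2 is the incidence of antibodies six months after treatment stopped.

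All patients are to be tested at baseline and at month 6. After that, "Only in case of positive antibodies measurements in previous visit follow-up measurements are planned after 1 year, 5 years and 10 years". The cut-off makes no reference to baseline status: "Positive antibodies are defined as values above 1.76". In addition, "Unscheduled visits will be excluded from the analysis".

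The analysis in section 4.7.1.1 is "The number and percentage of patients with positive anti-rhGH antibodies (ABs) will be tabulated by visit", together with a listing of all antibody results for patients who have a positive result.

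Three other places bear on this:

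- Section 4.1 sets baseline as the final visit of EP00-401 and includes "anti-rhGH antibody testing at final visit" among the data to be transferred.
- Section 2.1 sets the default denominator: "Percentages are routinely based on the total category count excluding the missing category if not otherwise mentioned". It also promises footnotes stating the base of each percentage.
- Section 4.7.1.2 plans a baseline comparison for other laboratory data: "Change from baseline (Shift from baseline) in hematology, biochemistry, thyroid function, and urinalysis parameters will be displayed by visit". Antibodies are not among them.

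**The concern.** The endpoint describes a change of state: a patient without antibodies at the end of treatment acquires them afterwards. The planned table describes a state at each visit. Because baseline is the last visit of the treatment study, a patient can enter follow-up already positive, and the retesting rule itself allows for positivity that persists. The month-6 percentage therefore mixes persisting with new positives.

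The later visits have a second problem. Testing there is planned only for patients positive at the previous visit. With missing results left out of the denominator, the percentages at year 1, year 5 and end of study mainly describe persistence among retested positives, and they cannot be set beside the month-6 figure.

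The SAP's introduction names immunogenicity, with diabetogenic potential, as a particular safety question of the study. Followed as written, the plan gives no count or percentage for the endpoint it defines, and a reader could take month-6 positivity for newly developed antibodies.

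**Working it through.** The SAP states no antibody rate, so there is no figure to reproduce. The check is whether the planned table determines the endpoint. **All counts below are assumed.**

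**1. Bounds from the by-visit table.** Let n patients be tested at both visits, b0 of them positive at baseline and b6 positive at month 6. The number of new positives can be anything from max(0, b6 − b0) to min(b6, n − b0).

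- n = 100, b0 = 5, b6 = 5: between 0 and 5 new positives, or 0/95 = 0% to 5/95 = 5.3% of baseline-negative patients.
- n = 100, b0 = 5, b6 = 8: between 3 and 8, or 3/95 = 3.2% to 8/95 = 8.4%.

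So showing baseline and month 6 side by side does not settle the number of new positives.

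**2. Size of the gap at month 6.** Let N be tested at both visits, P0 positive at baseline, r of those still positive, and c new positives.

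- Planned percentage = (r + c)/N
- New positivity among baseline negatives = c/(N − P0)
- Gap = (P0/N) × [r/P0 − c/(N − P0)]

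With N = 100, P0 = 4 and 4 positive at month 6, the planned table always shows 4.0%:

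| Still positive (r) | New (c) | New positivity | Gap (points) |
|---|---|---|---|
| 0 | 4 | 4/96 = 4.2% | −0.2 |
| 2 | 2 | 2/96 = 2.1% | +1.9 |
| 4 | 0 | 0/96 = 0% | +4.0 |

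The gap over a range of inputs, with new positivity held at 2%, in percentage points:

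| Positive at baseline | None persist | Half persist | All persist |
|---|---|---|---|
| 1% | −0.02 | 0.48 | 0.98 |
| 5% | −0.10 | 2.40 | 4.90 |
| 10% | −0.20 | 4.80 | 9.80 |

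For example, 10% at baseline with half persisting gives 0.10 × (0.50 − 0.02) = 0.048, or 4.8 points. The gap is zero if nobody is positive at baseline. It can also vanish by coincidence: with N = 100, P0 = 25, r = 1, c = 3, the planned figure is 4/100 = 4.0% and new positivity is 3/75 = 4.0%. Even then one of the four counted patients is not a new positive.

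**3. Later visits.** If 5 positives are retested and 4 remain positive, the default denominator gives 4/5 = 80%, whereas 4 of 100 patients is 4%.

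**4. Any visit against month 6 only.** Suppose 2 of 96 baseline negatives are positive at month 6 (2.1%). One further baseline-negative patient who missed month 6 and was first positive at a year-1 test outside the testing rule makes it 3/97 = 3.1%. On the planned schedule the two counts will be close, because a patient negative at both baseline and month 6 is not due for another test.

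**The case against.** The strongest reply is that section 2.2 asks for incidence at six months, and month-6 positivity can be read as answering that. The SAP's only definition of incidence, for adverse events in section 4.7.1.3, divides by the whole safety population, so a baseline-negative denominator is not prescribed. This stands as far as the denominator goes: it is a choice the SAP must state. It does not rescue the numerator, because section 2.3.2.1 speaks of patients developing antibodies, and the adverse-event section itself restricts its tables to events that began or got worse in EP00-402.

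Second, the information is not lost. The listing shows every result for each patient with a positive result, so new positives with a baseline result can be found by hand. The month-6 denominator can largely be rebuilt from the number tested minus the listed baseline positives. This also stands, and it limits the seriousness. But a hand reconstruction is not the number and percentage that the endpoint promises, and patients who were never positive and have no baseline result cannot be identified from the listing.

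Third, the retesting rule is stated openly and footnotes will name the percentage base. That discloses the later denominators but does not turn persistence into new development.

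Fourth, the lack of a shift table is not in itself a contradiction, since section 2.3.2.1 assigns shift from baseline only to the other laboratory parameters. That is correct; the mismatch lies between the antibody endpoint and its own table.

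Finally, every magnitude here is assumed, and the 9.8-point figure needs both extremes together. That is so, and the effect may be zero.

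**Conclusion.** The point holds: section 4.7.1.1 reports positivity at each visit, not the endpoint defined in section 2.3.2.1. No section separates patients already positive at baseline or plans a once-per-patient count of new positives.

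The size cannot be known from the SAP. It depends on the share positive at baseline and the share of those who stay positive; under the assumed inputs above it runs from −0.2 to 9.8 percentage points at month 6. For the later visits, the reading as persistence rests on the default denominator and the planned retesting rule. Tests done outside that rule at a scheduled visit would also count, and the SAP does not say whether antibodies were taken more widely at the last visit held after the study was terminated.

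The analysis is descriptive, so no test or decision changes. The plan should nonetheless be corrected, because in a descriptive safety study the reported percentage is the result.

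**What to change.** In section 4.7.1.1:

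- Add a once-per-patient number and percentage of new positives. The numerator is patients with a baseline result not above 1.76 and a result above 1.76 at any scheduled post-baseline visit. The denominator is baseline-negative patients with at least one scheduled post-baseline result.
- Show the month-6 result separately as well, which also serves the objective in section 2.2, and give patients without a baseline result their own category.
- Keep the by-visit table but split it by baseline status. Present year 1, year 5 and end of study as number positive over number tested, labelled as mainly retested earlier positives.

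The cost is SAP wording and one extra or changed table. The threshold is already set and the baseline antibody results are already transferred from EP00-401, so no new data are needed. The fix cannot recover conversions after month 6 in patients who were not retested; the label on the later visits should make that plain.
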